### 4.4. Pharmacokinetic Evaluation

Summaries of PK data will be described in a separate SAP.

### 4.5. Safety Analyses

Safety analyses will be conducted using the Safety Analysis Set.

#### 4.5.1. Study Drug Exposure

Exposure to study drug will be characterized by presenting descriptive statistics for duration of exposure (in months) and amount of study drug received (per dose and in total).

Descriptive statistics will be presented for the total duration of study drug exposure in months. The number and percentage of patients exposed for less than 3 months, 3 to <6 months, and so forth, will be presented. The number and percentage of patients exposed for at least 3 months, at least 6 months, and so forth, will be presented. Similar summaries will be presented for the number of doses received. The total number of patients requiring a dose reduction to 250 mg will be presented as well. Dosing information for each patient will be presented in a data listing.

#### 4.5.2. Adverse Events

All AEs will be summarized using the MedDRA coding system (Version 18.0 or later) and displayed in tables and data listings using SOC and preferred term.

Summaries of AEs will be performed for those events that are considered treatment-emergent, where treatment-emergent is defined per protocol as any AE with onset after the first administration of study medication, or any event that was present at baseline but worsened in intensity. Events with a fully or partially missing onset date will be assumed to be treatment-emergent unless it can be unequivocally determined (from the partial onset date and/or a partial or complete stop date) that the event occurred prior to the first administration of study medication.

All AEs will be summarized by the numbers and percentages of patients reporting a given AE. Therefore, in any tabulation, a patient contributes only once to the count for a given AE (overall, by SOC, by preferred term).

An overall summary of AEs will include the number and percentage of patients with any treatment-emergent adverse event (TEAE), any AE assessed by the Investigator as related to treatment (definite or possible relationship), any severe AE, any severe AE related to treatment, any serious adverse event (SAE), any SAE related to treatment, any AE leading to study treatment discontinuation, any AE leading to study treatment reduction, and any AE leading to death.

Tabulations by SOC and preferred term will be produced for all AEs, for all AEs related to study medication, for all SAEs, and for all AEs leading to study discontinuation. Separate tables will present AE incidence rates by maximum severity and by maximum relationship to study drug. Patients who report multiple occurrences of the same TEAE (preferred term) will be classified according to the most severe or most related occurrence, respectively. In all tables, AEs will be ordered by decreasing frequency of preferred term within SOC. AEs may also be summarized by other groups including, but not limited to, high level term (HLT), high level group term (HLGT) or standardized MedDRA query (SMQ).

Separate summaries will be provided for AEs of clinical interest, which include injection site reactions (ISRs) and hepatic AEs, including LFT abnormalities considered clinically significant by the Investigator.

The incidence of ISRs will be summarized by preferred term. A separate summary will present incidence rates by preferred term and maximum severity. Injection site reactions will be identified by the high level term of "Injection Site Reactions."

The incidence of hepatic events will be summarized by preferred term.

No formal hypothesis-testing analysis of AE incidence rates will be performed.

All AEs occurring on-study will be listed in patient data listings. Adverse events of clinical interest will also be listed separately.

By-patient listings will also be provided for the following: all AEs leading to death, all SAEs, AEs leading to study discontinuation, AEs leading to dose reduction, AEs leading to dose interruption, and AEs leading to withdrawal from drug. In addition, by-patient listings for any AEs leading to dose reduction, dose interruption, or withdrawal from study drug will be provided for those AEs mapped to the hepatic SMQ.

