1.5.1. Injection Site Reactions

ISRs have been observed in subjects receiving revusiran in completed and ongoing clinical studies. The majority have been mild or moderate in severity. Typically, the reactions consist of localized erythema, pain, swelling, pruritus, or rash at or around the injection site, and are transient in nature. Occasionally, these reactions have been of longer duration, more severe in nature and/or recurrent. In some subjects, this resulted in discontinuation of revusiran. If such reactions occur, rotation of the injection site (eg, to the extremities) is recommended as a potential mitigation strategy (see Section 6.5). Dose reduction may be considered in some cases after consultation with the Medical Monitor (see Section 3.5).

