9.3. Adverse Event Reporting

The Investigator is responsible for reporting all AEs that are observed or reported after administration of the first dose of study drug regardless of their relationship to study drug through the end of study (28 days after administration of the last dose of study drug).

All AEs must be recorded in the source records for the clinical study center and in the eCRF for the patient, whether or not they are considered to be drug-related. Each AE must be described in detail: onset time and date, description of event, severity, relationship to investigational product, action taken, and outcome (including time and date of resolution, if applicable).

For AEs that are considered AEs of clinical interest, additional clinical information may be collected based upon the severity or nature of the event.

If a patient has ISRs meeting any of the following criteria, the Investigator or delegate should contact the Medical Monitor and submit a supplemental ISR eCRF:

- ISRs that are recurrent and/or demonstrate a pattern of increasing severity
- Any ISR that is determined to be severe and/or a cause for study drug discontinuation
- Any ISR which, in the opinion of the Investigator, requires further medical evaluation or treatment

In some cases, where it is medically appropriate, further evaluation may include photographs, referral to a dermatologist, skin biopsy, or other laboratory testing. If a biopsy was obtained, the

Sponsor may request that the biopsy also be reviewed by a central dermatopathologist. To better understand the safety profile of the study drug, additional analysis of biopsy tissue may be performed according to local regulations.

For patients with hepatic AEs, additional information, including, clinical history, course of event, and local laboratory results to monitor LFT levels or other laboratory parameters, may be collected.

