9.5. Assessment of Severity

Adverse events are to be graded according to the categories detailed below:

Mild	Mild events are those which are easily tolerated with no disruption of normal daily activity.	
Moderate	Moderate events are those which cause sufficient discomfort to interfere with normal daily activities.	
Severe	Severe events are those which incapacitate and prevent usual activity.	

Changes in severity should be documented in the medical record to allow assessment of the duration of the event at each level of severity. Adverse events characterized as intermittent require documentation of the start and stop of each incidence. When changes in the severity of an AE occur more frequently than once a day, the maximum severity for the experience that day should be noted. If the severity category changes over a number of days, then those changes should be recorded separately (with distinct onset dates).

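### No planned table shows how often injection-site reactions recur, when they occur, how long they last or whether they worsen, although the protocol collects these data

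*SAP*

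**What the plan says.** The counting rule in SAP 4.5.2 applies to every adverse event table: "in any tabulation, a patient contributes only once to the count for a given AE (overall, by SOC, by preferred term"). Repeat occurrences of the same preferred term are classified by the most severe one.

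For ISRs the same section plans two tables. The first is patient incidence: "The incidence of ISRs will be summarized by preferred term". The second is by worst grade: "A separate summary will present incidence rates by preferred term and maximum severity". The event-level record goes into listings: "Adverse events of clinical interest will also be listed separately". There are also by-patient listings of "AEs leading to dose reduction, AEs leading to dose interruption, and AEs leading to withdrawal from drug". SAP 3.10 places all eCRF data in listings in date order, and SAP 3.2 adds the relative study day.

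The protocol looks beyond a first reaction. Section 1.5.1 says of ISRs: "Occasionally, these reactions have been of longer duration, more severe in nature and/or recurrent". Section 9.3 requires contact with the Medical Monitor and a supplemental ISR eCRF for, among other cases, "ISRs that are recurrent and/or demonstrate a pattern of increasing severity". Section 9.5 states: "Adverse events characterized as intermittent require documentation of the start and stop of each incidence". It also has severity changes over several days recorded as separate entries, each with its own onset date.

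**The concern.** The protocol deliberately collects recurrence, duration and escalation of ISRs, but the SAP has no table of event count, rate per dose, time of onset, duration, recurrence or use of the supplemental form. A count of patients ever affected says little about a reaction that can follow any of a long series of weekly injections.

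Safety and tolerability is the first secondary objective, and Protocol 1.2.2 describes ISRs as the most common drug-related events in the earlier studies. In the 10-dose Phase 2 study they were mild and led to no interruption or stopping of drug. In the long-term extension some recurred, lasted longer or grew more intense, and some led to interruption or discontinuation. The doses differed (5 or 7.5 mg/kg against 500 mg), so this does not establish an effect of longer exposure. It does make the pattern over repeated dosing a question worth a table.

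**Working it through.** The plan states no ISR rate and no figure for this point, so there is nothing of its own to reproduce.

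**1. Doses per completer** (Protocol 6.5; Table 1 for the last dose)
- Days 0 to 4: 5 doses. Day 7: 1 dose.
- Weeks 2 to 78: 78 − 2 + 1 = 77 doses. Week 78 as the last dose agrees with an End of Study visit at Week 82, about 28 days later.
- Total: 5 + 1 + 77 = 83 doses, or 166 injections at two per dose. If the last dose fell at Week 77, the total would be 82.

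**2. What the once-per-patient count could show**

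The per-dose ISR probability p is an assumption. With equal and independent risk at each dose, P(at least one ISR) = 1 − (1 − p)^83:

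| Assumed p per dose | Patients with at least one ISR |
|---|---|
| 0.5% | 34% |
| 1% | 57% |
| 2% | 81% |
| 3% | 92% |
| 5% | 98.6% |
| 10% | over 99.9% |

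Reaching 95% needs p = 1 − 0.05^(1/83), about 3.5%.

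Two features lower these figures:
- *Patients differ in susceptibility.* With a beta-binomial model and mean p of 5%, the proportion is 53%, 81% or 96% for a + b = 5, 20 or 100.
- *The table is by preferred term.* If p = 5% is split evenly over four terms, each row shows 1 − (1 − 0.0125)^83, about 65%.

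**3. A comparison that needs no assumed rate**

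Take 12 completers, so 12 × 83 = 996 doses and 12 × 1.5 = 18 patient-years. All ISRs are mild and of one preferred term, and none leads to a change in dosing.

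| | One ISR per patient | 20 ISRs per patient |
|---|---|---|
| Events | 12 | 240 |
| Planned incidence table | 12/12 | 12/12 |
| Planned maximum-severity table | 12/12 mild | 12/12 mild |
| Events per 100 doses | 100 × 12/996 = 1.2 | 100 × 240/996 = 24.1 |
| Events per patient-year | 12/18 = 0.67 | 240/18 = 13.3 |

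The planned ISR tables are the same in both columns, while the event rate differs 20-fold. For escalation, the maximum-severity table gives the worst grade reached but not whether grades rose over time.

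**The case against.** The strongest reply is that little is lost. With about 12 patients in a single arm, the by-patient ISR listing, in date order with relative study day, can be read patient by patient. The supplemental form is eCRF data and so is listed too. SAP 4.5.1 summarises the number of doses received, lists dosing for each patient and counts reductions to 250 mg. The SAP's tables follow the protocol's own adverse event plan (10.2.4.1), which promises no event rates. Medical Monitor contact and Data Monitoring Committee review operate whatever the tables contain. All of this stands, and it limits the point to a gap in summary tables. A listing still gives no rate, denominator or trend.

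A reader might infer three stronger things that the documents do not support:
- *That the ISR table will sit near 100%.* This needs a per-dose rate, and none is given. The range in the working starts at about a third of patients, and differing susceptibility, which recurrence in some patients would suggest, pulls it down.
- *That tolerable ISRs and ISRs that stop treatment would look alike.* SAP 4.5.2 counts patients with events leading to treatment discontinuation and to dose reduction, and tabulates events leading to study discontinuation by preferred term. Interruptions are listed, though not tabulated.
- *That the tolerability objective goes unanswered, or that recurrent ISRs are the main risk.* Those same summaries and listings address tolerability. ISRs are one of three risks in Protocol 1.5, and the recurrent or more severe form is called occasional.

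**Conclusion.** The point holds as a modest gap in reporting. No planned table gives ISR event count, rate per dose, timing, duration, recurrence or escalation, although the protocol collects the data for each. The working shows the size: ISR rates of 1.2 and 24.1 per 100 doses can yield the same planned ISR tables. That comparison rests on 83 doses per completer, 12 completers and reactions of one grade and one term with no dosing change. It does not depend on any assumed ISR risk. The actual patient-level incidence cannot be foreseen from the documents. The primary analysis is not touched.

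**What to change.** Keep the once-per-patient ISR tables and the discontinuation and dose-reduction summaries. Add to SAP 4.5.2:

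- ISR events per 100 doses administered, overall and by 3-month period. State the counting rule: because Protocol 9.5 records severity changes as separate entries, contiguous entries for one reaction are merged before counting.
- The number and percentage of patients with more than one ISR, and with a supplemental ISR form.

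Doses given are a better denominator than time, because the first period holds the daily doses: through Week 13 it has 5 + 1 + 12 = 18 planned doses, against 13 in Weeks 14 to 26. Duration and severity of successive ISRs can stay in the existing by-patient listing.

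The cost is a few descriptive tables and the programming of the merging rule. The adverse event records, the supplemental form and the dosing data are already collected, so no new data are needed.

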4.3. Study Drug Discontinuation

Patients are free to discontinue treatment at any time and for any reason, without penalty to their continuing medical care.

The Investigator or designee may discontinue dosing in a patient if the patient:

• Is in violation of the protocol

- Experiences a serious or intolerable AE
- Requires a prohibited medication
- Is found to be considerably noncompliant with the protocol-required visits

The Investigator will confer with the Sponsor or CRO Medical Monitor before discontinuing dosing in the patient. Patients who are pregnant will be discontinued from dosing immediately. In general, patients who discontinue study drug dosing for any reason will be encouraged to remain on the study to complete the remaining assessments through the 18-month visit so that their experience is captured in the final analyses; however, a patient may withdraw consent to participate in the study at any time. Patients who discontinue study drug may receive local standard of care treatment for their disease.

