4.4. Withdrawal Criteria

While patients who discontinue drug are encouraged to remain in the study to complete study assessments (Section 4.3), they are free to withdraw from the study at any time and for any reason, without penalty to their continuing medical care. Patients who withdraw or have a dose reduction before 6 months of study participation may be replaced. Patients will also be withdrawn if the study is terminated.

If a patient chooses to withdraw from the study, every effort should be made to conduct the Early Termination visit. When a patient withdraws from the study, the primary reason for discontinuation must be recorded in the appropriate section of the electronic case report form (eCRF) and all efforts will be made to complete and report the observations as thoroughly as possible.

The withdrawn patient will be asked to consent to either be contacted by telephone or to allow nonpatient contact follow-up (eg, medical record check) for up to 18 months after enrolling onto the study to document their overall health status.

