10.2.4.1. Adverse Events

Adverse events will be summarized by MedDRA System Organ Class and Preferred Term. Separate tabulations will be generated for treatment-emergent AEs (TEAEs), TEAEs by maximum severity, treatment-related AEs, SAEs, and discontinuation of study drug due to AEs. A patient listing will be produced for all AEs, deaths, SAEs, and AES leading to discontinuation of study drug.

10.2.4.2. Vital Signs, Clinical Laboratory Safety Tests, 12-lead Electrocardiograms, Physical and Ophthalmologic Examinations

For each continuous laboratory safety parameter (including, but not limited to, hematology, serum chemistry, coagulation, and urinalysis) results will be categorized as low, normal, or high based on the laboratory normal ranges. Shifts from baseline laboratory grade to the maximum

laboratory grades will be examined for key safety parameters. All out-of-range and clinically significant laboratory results will be identified in data listings. Descriptive statistics will also be provided as actual value and change from baseline over time.

Descriptive statistics for vital signs and ECG interval data will be presented by actual values and changes over time from baseline. Details of any abnormalities will be included in the data listings.

For ophthalmologic examinations, descriptive statistics of changes in eye examinations from baseline over time will be presented. Separate listings will be generated for any abnormalities noted during the eye examination.

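### The SAP's by-term adverse event table covers AEs leading to study discontinuation, where the protocol specifies discontinuation of study drug

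*SAP*

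**What the plan says.** Protocol 10.2.4.1 sets the level of summary: "Adverse events will be summarized by MedDRA System Organ Class and Preferred Term". It then names separate tabulations, among them "treatment-related AEs, SAEs, and discontinuation of study drug due to AEs".

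SAP 4.5.2 plans its SOC and preferred-term tables for all AEs, for related AEs, "for all SAEs, and for all AEs leading to study discontinuation". It describes no other by-term table of AEs that ended treatment or participation.

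On whether stopping drug means leaving the study, Protocol 4.3 says that "patients who discontinue study drug dosing for any reason will be encouraged to remain on the study to complete the remaining assessments"; these run to Month 18. Protocol 4.4 repeats the distinction: "While patients who discontinue drug are encouraged to remain in the study to complete study assessments", they remain free to withdraw.

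The SAP also keeps the two events apart. Its by-patient listings in 4.5.2 include "all SAEs, AEs leading to study discontinuation, AEs leading to dose reduction" and then, as a further item, "AEs leading to dose interruption, and AEs leading to withdrawal from drug". SAP 4.1 summarizes stopping study drug and withdrawing from the study as two separate disposition items, each with reasons. The overall AE summary in 4.5.2 counts patients whose study treatment was discontinued because of an AE.

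**The concern.** The protocol's tabulation answers the question of which events caused patients to stop revusiran. The SAP's table answers which events caused patients to leave the study. A patient who stops drug for an AE and then does what Protocol 4.3 encourages belongs in the first table but not in the second. The better that encouragement works, the fewer such patients appear in the SAP's table.

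These events are foreseeable. Protocol 1.5.1 and 1.5.2 report that injection site reactions and ALT/AST elevations led some subjects in other revusiran studies to stop treatment. Protocol 9.2.1.3 makes injection site reactions and hepatic AEs the events of clinical interest. The separate SAP summaries of these events give incidence (and severity for injection site reactions), but not whether the event ended treatment.

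At stake are a breakdown that the protocol names and the internal consistency of the safety tables. A reader who moves from the overall count to the by-term table could find fewer patients, or none, with no explanation.

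**Working it through.** The plan gives no figure to reproduce here. The check is a comparison of texts, followed by a small count.

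**1. Is the event the same?** Protocol 10.2.4.1 refers to discontinuation of study drug. The by-term table in SAP 4.5.2 refers to study discontinuation. The wording differs.

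**2. Could the two terms be synonyms?** Protocol 4.3 and 4.4 treat stopping drug and leaving the study as separate decisions. The SAP has separate listings for them in 4.5.2 and separate disposition items in 4.1. Within these documents they are not synonyms, and a programmer could reasonably build the table literally.

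**3. Where would a patient who stops drug for an AE and stays on study appear?**

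| SAP output | Captured? |
|---|---|
| Overall AE summary, AEs leading to treatment discontinuation (4.5.2) | Yes, count and percentage |
| Disposition, drug discontinuation by reason (4.1) | Yes |
| By-patient listing, AEs leading to withdrawal from drug (4.5.2) | Yes |
| Further listing of drug withdrawal for hepatic SMQ events (4.5.2) | Yes, if hepatic |
| SOC and preferred-term table of AEs leading to study discontinuation (4.5.2) | No |

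**4. How large is the gap?** Let s be the number who stop drug for an AE and k the number of those who stay on study. Assume the other s − k leave the study because of the AE. The overall summary shows s/N and the by-term table (s − k)/N. Take N = 12 (Protocol 3.2, approximate) and, purely as an illustration, s = 3:

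| k | Overall summary | By-term table |
|---|---|---|
| 0 | 3/12 = 25% | 3/12 = 25% |
| 1 | 3/12 = 25% | 2/12 = 16.7% |
| 2 | 3/12 = 25% | 1/12 = 8.3% |
| 3 | 3/12 = 25% | 0/12 = 0% |

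The overall figure is the same in every row. Only the by-term table moves, and it agrees with the overall summary only when nobody who stopped drug for an AE stayed on study.

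**The case against.** The strongest reply is that nothing is lost. SAP 4.5.2 says at its start that AEs are displayed in tables and listings by SOC and preferred term, so the withdrawal-from-drug listing should show the term for each such event. With about 12 patients, a reader could rebuild the missing table by hand. This stands, and it limits the point to one table.

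Second, the protocol does not say in so many words that each separate tabulation is by SOC and preferred term, and its synopsis refers only to discontinuations due to AEs. The overall summary therefore meets the commitment in part. This stands in part: by-term is the natural reading of 10.2.4.1, because the tabulations follow directly on the statement of that level.

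Third, the phrase may be a slip, since the overall summary in the same SAP section uses the treatment wording. The table shells that might settle it appear only as headings in the available text (SAP 7.1 and 7.4). That is possible, but a slip is a reason to correct the wording, and the separate listings rule out reading the terms as equivalent.

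A reader might also infer an undeclared departure from the protocol, because SAP 5 does not mention the change. That carries little weight. SAP 1.1.2 promises only substantial differences, SAP 5 lists no changes at all and defers to the study report, and one descriptive table is arguably below that threshold.

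**Conclusion.** The mismatch is real and should be corrected. As written, the by-term table would omit patients who stop drug for an AE and stay on study, and it would not reconcile with the overall AE summary.

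A reader might infer that the trial would understate its rate of drug discontinuation for AEs, or that its main tolerability result is at risk. The documents support neither. The overall summary, the disposition summary and the listing all keep these patients, so in the illustration the reported rate stays at 3/12, and the fall to 0/12 applies to the by-term table only. No text ranks this table above the other safety outputs.

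The conclusion assumes that the table is programmed as SAP 4.5.2 words it and that at least one patient stops drug for an AE and remains on study. If no patient does, the discrepancy does not arise. The illustrative 3 is not a forecast. No efficacy result is affected.

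**What to change.** In SAP 4.5.2, for the SOC and preferred-term tabulation only, change AEs leading to study discontinuation to AEs leading to study drug discontinuation. Keep AEs leading to study discontinuation as the by-patient listing already planned, and give the table the matching title.

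This aligns the by-term table with Protocol 10.2.4.1 and with the SAP's own overall count. It costs one word and a table title. No new data are needed, because the planned overall summary and listing already require AEs that stopped drug to be identified, and patient management is untouched.
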